1.2. Glossary of abbreviations

ALT	Alanine aminotransferase
ASCVD	Atherosclerotic cardiovascular disease
AST	Aspartate aminotransferase
BMI	Body mass index
CAD	Coronary artery disease
CVD	Cardiovascular disease
EAS	European atherosclerosis society
ESC	European society of cardiology
HDL	high-density lipoprotein
LDL	low-density lipoprotein
MI	Myocardial infarction
PCE	Pooled cohorts equation

1.3. Keywords

Statin Intolerance

Autonomy

Therapeutic Relationship

2. Introduction

2.1. Background

Statin therapy is an integral tool in the primary and secondary prevention of ASCVD. Higher compliance with their statin therapy is associated with a lower risk of mortality in a step-wise manner (1). Despite this, rates of statin compliance are abysmally low. Prior studies suggest that less than 40% of primary prevention patients are compliant with their prescribed statin therapy. Individuals who have suffered a prior MI have an incremental improvement in compliance to around 60%. Younger individuals and women appear to have exceptionally low rates of compliance to statin therapy (2). Low rates of compliance remains a significant barrier to reducing the burden of ASCVD, with some suggesting efforts to increase compliance can have an oversized impact on reducing rates of ASCVD (3).

On the other hand, patients often prefer “natural” therapies over conventional medicine for a variety of reasons (6). Monacolin-K is a naturally occurring molecule in red yeast-rice extract, a commonly used health supplement. It is structurally identical to lovastatin and has been shown to reduce LDL-C levels and ASCVD events in randomized placebo controlled trials (7, 8).

Patient autonomy is a core bioethical principle affirming the right of the patient to determine the trajectory of their health care at times. This bioethical principle has been referred to as “first among equals”, implying that it is the most important bioethical principle (4). The role of autonomy in patient compliance is not entirely clear, but there is evidence that suggests that increased patient autonomy in the decision-making process can result in higher rates of long term compliance (5).

3. Study objectives

Primary Objective

The objective of this study is to determine if introducing autonomy in the decision-making process will increase statin compliance and reduce the rate of perceived side effects from statin use.

Rationale for the study

[figure not shown]
- 1) Statin use has been repeatedly shown to reduce the risk of ASCVD events
- 2) Patient compliance is a significant and often insurmountable barrier to statin therapy
- 3) Increased patient autonomy may be associated with greater rates of long-term compliance and warrants further investigation

Study hypotheses

Patients who perceive a higher degree of autonomy in the decision-making process are more likely to be compliant with statin therapy and less likely to perceive side effects from statin therapy.

4. Study design

1.1. Study overview diagram

4.2 Study protocol:

Patients meeting the study criteria will be enrolled at outpatient cardiology clinics at four centers: Lithuanian University of Health Sciences, Northway Medical Centre, Prienu Hospital, and Unomeda Medical Centre. The enrolment period will last six months, with an estimated 50 patients per month enrolled into the study, for a total of 300 patients.

Patients will be randomized to either the control group or the intervention group. Baseline variables will include demographic variables (age, gender, BMI, blood pressure, heart rate), medical history (hypertension, hyperlipidaemia, type 2 diabetes mellitus, tobacco use), laboratory variables (total cholesterol, HDL, LDL, triglycerides, AST, ALT, creatine kinase, and, vitamin D levels) and socioeconomic variables (education level, income level, rural or urban, and marriage status).

The control group will be provided reassurance through a short, semi-structured discussion on the excellent safety profile of statins, similar to a typical interaction between a clinician and patient. They will then be prescribed 30mg atorvastatin daily as a 30 tablets supply with five patient-initiated re-fills for 30 tablets each. Final follow-up in this group will occur at 6 months.

The intervention group will be offered a red yeast rice extract 20mg nightly to achieve a goal LDL-cholesterol of <2.6 mmol/L (100 mg/dL) in accordance with the 2019 ESC/EAS guidelines (9). Initial follow-up will take place in 2 months to assess the efficacy of their treatment. Patients who are not at the goal LDL-cholesterol will be prescribed 30mg atorvastatin nightly as a 30 tablets supply with five patient-initiated re-fills for 30 tablets each, with final follow-up after 6 additional months. Patients who are at goal on the red yeast rice extract will be recommended to switch to lovastatin 20mg nightly as a bio-identical substitute, but they will be excluded from further analysis.

In both groups, statin adherence will be assessed by pharmacy refill records at the final follow-up. A short, four question questionnaire (Appendix A) will be administered at this point as well. Final follow-up laboratory variables collected will include total cholesterol, HDL, LDL, triglycerides, AST, ALT, creatine kinase, and vitamin D levels.

Conversation guidelines for each clinical encounter in the intervention group are included in Appendix B.

Randomisation

Patients will be randomized by block randomization. On the first week of enrollment, the clinician will only enroll patients into the control arm. On the subsequent week, the clinician will only enroll patients into the intervention arm.

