1.1. Study summary

Design

Patients will be randomized to receive either 30mg of atorvastatin or be presented with a choice of receiving either a “natural” statin (red yeast rice extract) or 30mg of atorvastatin.

In the intervention arm, a goal of either LDL-C reduction of at least 50% or an LDL-C < 100 mg/dl will be discussed on the initial visit. Goals will be re-assessed at 2 months, if goals are not met, patients will be given 30mg of atorvastatin.

Aims

To assess if introducing greater patient autonomy increases patient compliance with statin therapy.

Outcome measures

The primary endpoint will be 6-month compliance of statin therapy, after the initiation of atorvastatin.

Secondary endpoints will be rates of perceived side effects from statin use, including myalgias, fatigue, mental fog and GI upset.

Population

This will be a multi-center study of 300 pts, 150 in each arm.

Eligibility

Primary prevention (no history of CAD, MI, or stroke) patients with a moderate 10-year ASCVD risk who decline statin therapy.

Duration

Anticipated recruitment is 6 months. Follow-up will be performed at 6 months in the control arm and 2 and 8 months in the intervention arm, for a total study duration of 14 months.

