4.3. Study outcome measures

Primary Endpoint

Rate of statin compliance, based on pharmacy refill records. Values per patient can range from 0-6 according to the number of refills.

Secondary Endpoints:

Rate of perceived side-effects from statin use, including muscle aches, fatigue, mental fog, and gastrointestinal upset.

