9.2. Consent

Consent to enter the study must be sought from each participant only after a full explanation has been given, an information leaflet offered and time allowed for consideration. Signed participant consent should be obtained. The right of the participant to refuse to participate without giving reasons must be respected. After the participant has entered the study the clinician remains free to give alternative treatment to that specified in the protocol at any stage if he/she feels it is in the participant's best interest, but the reasons for doing so should be recorded. In these cases the participants remain within the study for the purposes of follow-up and data analysis. All participants are free to withdraw at any time from the protocol treatment without giving reasons and without prejudicing further treatment.

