Appendix A Final Follow-up questionnaire

Have you had any of the following symptoms from atorvastatin over the past 6 months?			
Myalgias (muscle aches)	 Yes	 No	 Not Sure
Fatigue	 Yes	 No	 Not Sure
Mental fog (slow thinking or memory issues)	 Yes	 No	 Not Sure
Gastrointestinal upset	 Yes	 No	 Not Sure

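### Statin-safety reassurance is written in for controls only: an avoidable difference between arms that may mask, not create, a benefit on self-attributed side effects (minor)

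*Protocol*

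**What the plan says.** The aim in section 1.1 is "To assess if introducing greater patient autonomy increases patient compliance with statin therapy". Section 3 puts it as a causal question, "The objective of this study is to determine if introducing autonomy in the decision-making process will increase statin compliance", and the same sentence adds a reduction in perceived side effects.

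On what each arm is told, section 4.2 says of controls: "The control group will be provided reassurance through a short, semi-structured discussion on the excellent safety profile of statins". It likens this to an ordinary consultation. Atorvastatin is then prescribed. Appendix B gives the control encounter three points: acknowledge reluctance, reassure on long-term safety, reassure on long-term efficacy.

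The intervention guide in Appendix B has four points at the first visit (reluctance, LDL goal, the natural option as an open question, review at two months). It has one point at two months for patients above goal: the supplement has not worked, so change to the statin to lower cardiovascular risk. None of these concerns statin safety.

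The secondary endpoint in section 4.3 is "Rate of perceived side-effects from statin use, including muscle aches, fatigue, mental fog, and gastrointestinal upset". Appendix A collects it by asking "Have you had any of the following symptoms from atorvastatin over the past 6 months", with yes, no or not sure for each of four symptoms.

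**The concern.** The objective attributes any difference in perceived side effects to autonomy in the decision. Reassurance about safety is a separate ingredient: a clinician can offer a choice with it or without it. As written, it goes with the control arm alone, so reassurance and absence of choice coincide. No later analysis can separate two features that are fully aligned with arm.

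The endpoint is of a kind that such a message could reach. The patient judges whether a symptom came from the drug, and the patients were enrolled because they decline statins. They know what they were offered. The protocol does not use the word unblinded, but allocation alternates by week and the only blinding it states is of the Clinical Events Committee. What a patient was told about safety when starting the drug may affect what is later blamed on it. That link is an assumption; the documents give no evidence or figure for it.

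What is at stake is a missed benefit. If reassurance lowers reported symptoms, it does so in controls only and narrows the gap that the trial hopes to see.

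**Working it through.** The protocol gives no figure on this point, neither a side-effect rate nor an effect of reassurance, so there is nothing to reproduce. The check is a comparison of text, followed by an illustration.

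**Step 1: what is written for the encounter at which atorvastatin starts**

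| Patient | Encounter | Points up to then | On safety |
|---|---|---|---|
| Control | First visit | 3 | 1 |
| Intervention, above LDL goal | Month 2 | 4 + 1 = 5 | 0 |
| Intervention, chooses atorvastatin at once | First visit | 4 | 0 |

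The third row rests on section 1.1, which allows that choice. Section 4.2 and Appendix B do not set out the pathway. Patients at goal on red yeast rice are left out of the table because section 4.2 says of them "but they will be excluded from further analysis". The counts show where the safety message is written and where it is not. They do not measure how much reassurance anyone receives.

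**Step 2: direction and possible size (all inputs assumed)**

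Let the offered choice have risk ratio *c* on reported symptoms and reassurance have risk ratio *r*, acting multiplicatively. With reassurance in controls only:

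observed ratio = *c* / *r*

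Take *c* = 0.80 and an assumed symptom rate of 30% with neither choice nor reassurance. The intervention rate is 0.80 × 30% = 24%, and the difference due to choice is 24 − 30 = −6 points.

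| *r* | Control rate | Observed ratio | Observed difference |
|---|---|---|---|
| 1.00 | 30% | 0.80 | −6 points |
| 0.95 | 28.5% | 0.80/0.95 = 0.84 | −4.5 points |
| 0.90 | 27% | 0.80/0.90 = 0.89 | −3 points |
| 0.80 | 24% | 0.80/0.80 = 1.00 | 0 points |

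The last row reaches 1.00 only because reassurance is assumed to be exactly as strong as the choice. With *r* = 1.00 nothing is masked.

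**Step 3: the same message in both arms**

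The ratio becomes (*c* × *r*) / *r* = *c*. For *r* = 0.90 the rates are 0.90 × 24% = 21.6% and 27%, and 21.6/27 = 0.80. Under the multiplicative assumption, the masking disappears whatever the value of *r*.

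**The case against.** The strongest reply is that the reassurance is the comparator. Section 4.2 presents the control talk as ordinary care, and the trial sets persuasion against an offered choice. A comparison of usual care with a package is defensible. It is not, however, the stated objective, and the remedy leaves the control talk as it is. Nor could the objective simply be restated as a comparison of whole strategies, since at-goal intervention patients are dropped from the analysis.

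A second reply is that what is not written may still be said. This stands in part. Appendix B offers guidelines and sample conversations and does not forbid a safety message in the intervention arm. Section 9.2 also applies to everyone: "Consent to enter the study must be sought from each participant only after a full explanation has been given, an information leaflet offered". The real imbalance may therefore be smaller than the text suggests. But consent information at entry is not the same as reassurance at the visit where the drug is prescribed, which comes two months later for patients who start on red yeast rice.

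Third, the effect is conservative, falls on a secondary endpoint and has no size in the documents. All of this stands and limits the weight of the point.

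Fourth, equal reassurance would not isolate autonomy. This also stands: the LDL goal, the extra visit, prior red yeast rice and the at-goal exclusion would still differ between arms.

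**Conclusion.** The asymmetry is certain from the text; its consequence is not. Reassurance on statin safety is written in for controls only, this is not needed in order to offer a choice, and it may lower self-attributed side effects in that arm alone. The expected direction, if reassurance works as intended, is to mask a benefit of the intervention. The size is unknown, and the illustrated range of 0.84 to 1.00 for a ratio of 0.80 rests entirely on assumed inputs. Severity is minor.

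A reader might infer more, and the documents do not support it:

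- **That the difference could produce a false benefit on side effects.** Reassurance that works favours control.
- **That intervention patients hear nothing about safety.** The guide is silent, but it is only guidance, and section 9.2 requires a full explanation for all.
- **That the primary endpoint is compromised.** It is a count of pharmacy refills, not a self-attributed symptom, and nothing in the protocol shows or sizes an effect of the safety talk on refills.
- **That equal reassurance would make this a test of autonomy.** The hypothesis is about perception, "Patients who perceive a higher degree of autonomy in the decision-making process are more likely to be compliant with statin therapy", yet none of the listed outcomes or questionnaire items measures perceived autonomy, and the other differences between arms remain.

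**What to change.** In Appendix B, add the control guide's safety reassurance point and its matching long-term efficacy point to the intervention encounter at which atorvastatin is prescribed. That is month 2 for patients above the LDL goal, or the first visit for a patient who chooses atorvastatin then. Leave the control talk unchanged.

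Word the conclusions as the effect of the offered-choice approach, including its LDL goal and two-month visit, in the patients analysed, and not as the effect of autonomy alone.

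The cost is two added lines in the guide and some care in reporting. No extra visits, tests or patients are needed. The downside is a slightly longer intervention conversation.

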Appendix B

Clinical Encounter Conversation Guidelines

Control Group Initial Encounter

Point(s) to discuss

1. Acknowledge the patient's reluctance to start statin therapy
2. Reassure the patient that long term data supports the safety of statins
3. Reassure the patient that long term data supports the efficacy of statins

Sample Conversation(s):

"I understand that you are hesitant to start statin therapy. We over two decades of long-term follow-up data regarding statin use. The data clearly shows that statins are extremely safe and patients who stay on statins live longer and healthier lives."

Intervention Group Initial Encounter

Point(s) to discuss

1. Acknowledge the patient's reluctance to start statin therapy

2. ESC/EAS 2019 guidelines recommend an LDL-cholesterol < 2.6 mmol/L (100 mg/dL)
3. Present the option of a natural supplement as an open-ended question
4. The impact of the therapy will be assessed in two months

Sample Conversation(s):

“I understand that you are hesitant to start statin therapy. According to European guidelines, your LDL-cholesterol should be less than 2.6 mmol/L (100 mg/dL) to reduce your risk of a cardiovascular event. What is your opinion on trying a natural supplement to reduce your cholesterol?”

If the patient agrees to red yeast rice extract

“Let's follow up in two months to see if our LDL-cholesterol goals have been met”

Intervention Group Initial Follow-up

If LDL-cholesterol > 2.6 mmol/L (100 mg/dL)

Point(s) to discuss

1. Since the natural remedy did not work, we should switch to the statin to reduce cardiovascular events

Sample Conversation(s):

“Unfortunately, we were not able to meet our goals with the natural supplement. Because of this, let's try the prescription medicine instead (atorvastatin 30mg nightly)”

If LDL-cholesterol < 2.6 mmol/L (100 mg/dL)

Point(s) to discuss

1. The natural remedy did reduce your LDL-cholesterol to our original goal
2. However, the effect of the natural remedy is unreliable over time due to lack of regulation

3. Let's switch to a bio-identical prescription medicine for reliability

“Congratulations, we were able to meet our goal using a natural supplement. This supplement contains naturally occurring lovastatin; however it is difficult to predict the dose that you are receiving since supplements are not regulated. Let's try a medium dose of lovastatin instead (20mg lovastatin nightly)”

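### In the visible text no AST, ALT or CK result is scheduled at month 2, when the next statin is prescribed on LDL-C alone

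*Protocol*

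**What the plan says.** Section 4.2 of the Protocol lists AST, ALT and CK among the baseline variables and again at the end: "Final follow-up laboratory variables collected will include total cholesterol, HDL, LDL, triglycerides, AST, ALT, creatine kinase, and vitamin D levels". Between these, the intervention arm has one visit: "Initial follow-up will take place in 2 months to assess the efficacy of their treatment".

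What follows that visit depends on LDL-C. Section 1.1 states: "Goals will be re-assessed at 2 months, if goals are not met, patients will be given 30mg of atorvastatin". For the others, section 4.2 says: "Patients who are at goal on the red yeast rice extract will be recommended to switch to lovastatin 20mg nightly as a bio-identical substitute", and adds "but they will be excluded from further analysis". The month-2 conversation guide in Appendix B branches on LDL-C in the same way and contains no safety check. Section 7 sets clinic visits at month 6 (control) and months 2 and 8 (intervention), and asks only that the CRF be completed.

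Section 6.1 defines statin intolerance as a CK increase, AST/ALT above three times the upper limit of normal, or rhabdomyolysis, linked to starting a statin during the study. Section 5.4 withdraws such patients from the study. Section 9.2 lets clinicians depart from protocol treatment and keeps those patients in follow-up and analysis.

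**The concern.** The protocol has a laboratory-based intolerance rule with a mandatory consequence. At its only interim visit, where a new statin prescription is issued, it schedules none of the tests that the rule uses. A patient whose enzymes had risen on red yeast rice could go straight on to atorvastatin or lovastatin without the prescriber knowing.

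The point is stronger for atorvastatin, which is a different statin. With lovastatin the patient continues what the protocol regards as the same molecule. Attribution also suffers: if the only panels are at baseline and month 8, a rise seen at month 8 cannot be assigned to the supplement or to the drug that followed it.

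What is at stake is patient safety and the workability of 5.4. Laboratory values are not an endpoint, so this is not a claim about the primary result.

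**Working it through.** The plan gives no figure to reproduce, so the check is of the text, with simple counts.

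**Step 1. Scheduled AST/ALT/CK panels (sections 4.2 and 7).**

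| Arm | Baseline | Month 2 | Final follow-up |
|---|---|---|---|
| Control | yes | no visit | month 6 |
| Intervention | yes | visit, panel not listed | month 8 |

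Scheduled panels at month 2: 0. If section 7 covers the whole intervention arm, the first post-baseline panel comes 8 − 2 = 6 months after red yeast rice ends. For at-goal patients, who leave the analysis, it is not stated whether that panel is still taken.

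**Step 2. Why month 2 in particular.** Controls also have only one post-baseline panel. But their atorvastatin is prescribed when baseline bloods are collected. In patients who take red yeast rice first, the latest scheduled panel before the next statin is two months old and predates the supplement. A blood sample at month 2 is implied by the LDL-C decision.

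**Step 3. Is red yeast rice statin exposure in the protocol's own terms?**
- In favour: section 1.1 labels it a natural statin. Section 2.1 describes its active molecule as structurally the same as lovastatin. Appendix B says it contains lovastatin and that "it is difficult to predict the dose that you are receiving since supplements are not regulated".
- Against: Appendix B also sets the two apart: "Since the natural remedy did not work, we should switch to the statin to reduce cardiovascular events". Section 1.1 counts the primary endpoint from the start of atorvastatin.
- Result: the first reading is better supported, but 6.1 does not settle it.

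**Step 4. The CK criterion.** In 6.1 the threshold of three times the upper limit follows AST/ALT. CK can be read as sharing it, or as meaning any increase. Adding CK tests without resolving this could trigger the rule on a trivial rise.

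**Step 5. Size of the change.** Section 1.1 says "This will be a multi-center study of 300 pts, 150 in each arm". Let p be the share of the intervention arm taking red yeast rice up to month 2, which the protocol does not give.
- Extra assays = 150 × p × 3.
- p = 1: 150 × 3 = 450. p = 0.5 (illustration only): 225.

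No rate of enzyme rise is given, so the number of patients meeting 6.1 cannot be estimated. Each percentage point meeting it would be at most 150 × 0.01 = 1.5 patients.

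**Step 6. What the remedy could do to the primary endpoint.** Refills run from 0 to 6 (section 4.3). Assume that compliance is refills divided by 6, and that a patient whose atorvastatin is withheld scores 0 instead of the 50% average assumed in 4.5. Each such patient lowers the intervention mean by 50 / 150 = 0.33 percentage points with 150 analysed. With the minimum of 138 / 2 = 69 per arm, the figure is 50 / 69 = 0.72 points. The planned detectable difference is 5 points. A handful of withheld prescriptions would therefore be visible, and in one arm only.

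**The case against.** The strongest reply is that this is an absence, not a contradiction. Sections 5.4 and 6.1 set no testing time, and a withdrawal rule triggered by events can stand without an interim panel. That is fair, and it limits the point to a suggested improvement.

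A reader might infer more: that the intolerance rule cannot be applied at all before the switch, or that the protocol sends patients known to be intolerant on to another statin. The documents do not support either. No text forbids an unscheduled test, section 9.2 lets the clinician change treatment, and the study diagram and CRF, which are not shown, might list month-2 tests. Yet freedom to act does not supply the result on which to act, and no visible text schedules it.

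Two further objections stand in part. Section 6.1 does not clearly bring red yeast rice within its scope, so it is too strong to say that the protocol already requires such a patient to stop; the definition needs a sentence. And a month-2 panel leaves six months of atorvastatin without an interim test, as in controls. It improves one decision and does not create continuous monitoring.

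The cost to the endpoint is also real. The check exists in one arm only and can produce zero refills by clinician decision. It has to be declared and handled.

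**Conclusion.** The point holds in limited form: as scheduled in the visible text, no AST, ALT or CK result is available when the month-2 prescription is made, so the laboratory part of 6.1 and 5.4 cannot be applied from scheduled data at that visit. It is a minor patient-safety improvement, worth considering because it is cheap.

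It rests on three assumptions: that the diagram and CRF do not schedule these tests, that red yeast rice is meant to count as statin exposure, and that blood is drawn at month 2 for LDL-C. No claim is made about how many patients are affected. The arm size of 150 is only a ceiling, since section 1.1 lets intervention patients choose atorvastatin at the outset and they would not face this switch. Nor is it claimed that the missing tests bias the primary endpoint.

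**What to change.** 1. **Section 4.2:** for patients taking red yeast rice, add AST, ALT and CK to the month-2 sample already needed for LDL-C, and review the results before prescribing atorvastatin or lovastatin.
2. **Section 6.1:** state that red yeast rice counts as statin exposure, and give CK an explicit multiple of the upper limit of normal. The present wording does not determine the multiple; the sponsor should choose it on clinical grounds.
3. **Section 5.4, both arms:** a patient who meets the definition stops the drug but stays in follow-up and analysis. This matches section 9.2 and avoids the bias from removing patients because of a result that arises after allocation.

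The cost is a protocol amendment and at most 450 assays, fewer in practice, in a trial that section 9.7 says is unfunded. No extra visit is needed. The month-2 values exist in one arm, so they should be reported descriptively. Because the check is one-sided, count and report the patients whose atorvastatin was withheld and the refills missed for that reason, and examine their influence in a sensitivity analysis of the primary endpoint. The exclusion of at-goal patients from analysis is a separate matter that this change leaves as it is.

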4.5. Sample size/Power calculation

This study is designed as a superiority trial. Based on prior literature, we estimate a 50% statin compliance rate with a standard deviation of 10% (2). We will set the minimal detectable effect at a 5% increase in statin compliance, with an $\alpha < 0.05$ and power of 0.9. Based on case-to-control ratio of 1:1, our total minimum sample size for the primary endpoint is 138. However, we will plan on a total sample size of 300 patients, to account for patients who drop out of the study as well as patients who will be excluded due to attaining an LDL-cholesterol of <2.6 mmol/L (100 mg/dL) on red yeast rice extract.

5. Participant entry

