5.2. Inclusion criteria

1. Over 40
2. Moderate ASCVD risk
3. Decline statin therapy

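### Intervention patients who reach the LDL goal on red yeast rice are dropped from the analysis; this one-arm exclusion after assignment biases the primary comparison, probably against the intervention

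*Protocol*

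**What the plan says.** Under section 4.2, controls are prescribed atorvastatin at entry and have one follow-up visit, at 6 months. Intervention patients are offered red yeast rice and have LDL checked at 2 months. Those not at goal are prescribed atorvastatin and followed for 6 more months. Those at goal "will be recommended to switch to lovastatin 20mg nightly as a bio-identical substitute, but they will be excluded from further analysis". Section 4.5 gives, as one reason for enlarging the trial, "patients who will be excluded due to attaining an LDL-cholesterol of <2.6 mmol/L (100 mg/dL) on red yeast rice extract".

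Four other places bear on this:

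- **Section 1.1 (Study summary), goal.** It differs from that in 4.2: "a goal of either LDL-C reduction of at least 50% or an LDL-C < 100 mg/dl will be discussed on the initial visit". Sections 4.2 and 4.5 and Appendix B use only the 100 mg/dL threshold.
- **Section 1.1, endpoint.** "The primary endpoint will be 6-month compliance of statin therapy, after the initiation of atorvastatin". Section 4.3 instead speaks of statin compliance from pharmacy refill records: "Values per patient can range from 0-6 according to the number of refills".
- **Section 5.2.** Entry requires age over 40, "Moderate ASCVD risk" and declining a statin. There is no minimum LDL.
- **Appendix A.** The final questionnaire asks "Have you had any of the following symptoms from atorvastatin over the past 6 months", so it does not cover a patient moved to lovastatin.

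**The concern.** Whether an intervention patient is analysed depends on an LDL value measured 2 months after assignment. Controls face no such test. A control who would have reached goal on the supplement stays in, while the matching intervention patient is removed, so the groups compared are not the groups assigned.

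The selection is plausibly related to the outcome. Reaching goal generally requires taking the supplement, and people who take one preparation reliably may well refill another. If so, the exclusion removes better adherers from the intervention arm alone, and a real benefit is understated or missed. Baseline LDL and drug response also decide who is at goal. With no LDL floor in 5.2, a patient who starts red yeast rice already below the threshold can be excluded while an identical control is kept.

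The rule also sits badly with the trial's own aims. The objective in section 3 is statin compliance, and a goal attainer who moves to lovastatin is taking a prescribed statin after being given a choice. Section 9.2 keeps patients whose clinician changes their treatment in the data analysis, which is the opposite principle.

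**Working it through.** **The plan's own figure.** Inputs from 4.5: difference 5 points, SD 10 points, alpha 0.05, power 0.9, ratio 1:1. Per arm, n = 2 × SD² × (z_alpha + z_power)² / difference².

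- One-sided: 2 × 100 × (1.645 + 1.282)² / 25 = 68.5, so 69 per arm and 138 in total. This is the stated figure.
- Two-sided: 2 × 100 × (1.960 + 1.282)² / 25 = 84.1, so 85 per arm and 170 in total.

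With 150 per arm, the intervention arm could lose 81 patients (54%) and keep 69, or lose 65 (43%) and keep 85. Numbers are therefore not the difficulty.

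**Bias in general.** Let q be the share of the intervention arm excluded and g the mean compliance of goal attainers minus that of the others. The retained mean differs from the full-arm mean by −q × g, whatever the sample size. The protocol gives neither q nor g.

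**Assumed model.** Each patient has a propensity p to take the supplement, with mean 0.5 (the 50% in 4.5). The chance of being at goal is c × p, with c = 0.4, 0.6 or 0.8, so q = 20, 30 or 40%. If the same p drives later refills,

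bias = E[p(1 − cp)] / (1 − cE[p]) − E[p] = −c × Var(p) / (1 − c × E[p]).

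At SD 10%, Var(p) = 0.01:

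- c = 0.4: −0.004 / 0.8 = −0.50 points
- c = 0.6: −0.006 / 0.7 = −0.86 points
- c = 0.8: −0.008 / 0.6 = −1.33 points

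In the general form these correspond to g of only 2.5, 2.9 and 3.3 points.

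**Power** (true difference +5, SD 10, two-sided 5%, normal approximation): SE = 10 × √(1/150 + 1/n), with n the retained intervention patients; power = Φ(expected difference / SE − 1.96).

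| Excluded | n retained | SE | Power, numbers lost only | Expected difference with bias | Power with bias |
|---|---|---|---|---|---|
| 0% | 150 | 1.155 | 99% | 5.0 | 99% |
| 20% | 120 | 1.225 | 98% | 4.5 | 96% |
| 30% | 105 | 1.272 | 98% | 4.1 | 90% |
| 40% | 90 | 1.333 | 96% | 3.7 | 79% |

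Simulating 4,000 trials with the exclusion applied gave power of 95/90/77% and mean estimates of +4.5/+4.1/+3.6.

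**Sensitivity.** Bias in points for 20/30/40% excluded. The columns other than the shared propensity link the two behaviours by a Gaussian copula (1,000,000 draws).

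| Spread of adherence | Shared propensity | Correlation 0.5 | Correlation 0 | Correlation −0.3 |
|---|---|---|---|---|
| SD 10% (protocol) | −0.5/−0.9/−1.3 | −0.25/−0.4/−0.7 | 0 | +0.15/+0.3/+0.4 |
| Beta(2,2), SD 22% | −2.5/−4.3/−6.7 | −1.2/−2.1/−3.3 | 0 | +0.7/+1.3/+2.0 |
| Uniform, SD 29% | −4.2/−7.1/−11.1 | −2.0/−3.5/−5.4 | 0 | +1.2/+2.1/+3.2 |

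At SD 10% and correlation 0.5, two-sided power is 97/95/90%.

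**The case against.** Nobody can dispute that the exclusion is there; the case against concerns its size, its direction and the remedy.

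- **Size.** At the protocol's own SD the harm may be modest. With correlation 0.5, power still meets the 0.9 target at 40% excluded. On the one-sided basis that reproduces 138, even the shared-propensity case keeps 98/95/87%. The large biases need SDs of 22% or 29%, which the protocol does not state. All this stands. It limits the claim about size, but it does not make the comparison sound.
- **Direction.** Poor adherers given red yeast rice may not return at 2 months and so never enter the refill count, which would favour the intervention. This is a separate mechanism, but it is a fair reason to say probably and no more.
- **Estimand.** One could argue that the target is atorvastatin compliance among those who start it, as 1.1 implies. That fails because the control arm is not restricted in the same way. Baseline LDL cannot identify the controls who would have taken the supplement and responded.
- **LDL goal.** Section 1.1 states a treatment goal and does not mention exclusion. True, but 4.2 excludes those at goal, so two versions of the goal leave it unclear who is excluded.
- **Remedy.** A goal attainer who stays on red yeast rice would score 0 for statin dispensing, and no control can score 0 by that route. This is a real consequence. It follows from an endpoint of prescribed-statin compliance and should be stated openly. The same rule also scores those lost before month 2.

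**Conclusion.** The concern holds. As written, the primary analysis compares a selected intervention group with an unselected control group, and the increase to 300 patients does not address that. This must be fixed.

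The existence of the selection follows from the text alone. Its direction, probably against the intervention, rests on the assumption that people who take the supplement also tend to refill a statin. Its size rests on an assumed 20–40% excluded and on the models above. At the protocol's SD it is at most 1.3 points of the planned 5. With the wider Beta(2,2) spread, a shared propensity and 40% excluded, it exceeds the whole planned effect. The protocol supplies neither the share at goal nor the link between the two behaviours, and the planned analysis cannot correct for them.

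**What to change.** 1. In 4.2, delete the clause that removes goal attainers from analysis, and delete the matching reason in 4.5. State that all assigned patients are analysed in their arm.
2. Define compliance as dispensings of any prescribed statin, from the pharmacy records already planned, over a stated 6-month window: months 0–6 for controls and for intervention patients who choose atorvastatin at entry, months 2–8 for those who start with red yeast rice. No statin dispensed in the window scores 0 in either arm.
3. Section 4.2 gives no supply or refill count for lovastatin, so the 0–6 score in 4.3 is undefined for these patients. Use a common scale, such as proportion of days covered.
4. Bring the endpoint wording in 1.1 and the question in Appendix A, both now limited to atorvastatin, into line.
5. Keep the analysis without goal attainers only as a labelled sensitivity analysis.
6. Reconcile the LDL goal in 1.1 with that in 4.2, 4.5 and Appendix B. Which goal applies is a clinical decision for the sponsor. Items 1 to 5 change no treatment.

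The cost is wording in 1.1, 4.2, 4.3, 4.5 and Appendix A, plus final pharmacy records and the questionnaire for patients moved to lovastatin. The price in interpretation is that the intervention score pools atorvastatin and lovastatin fills. The change should be made before patients reach the 2-month visit, because data on those not followed after it may not be recoverable.
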